5.6 Descriptive Statistics

All continuous variables will be summarized by presenting the number of subjects ('n'), mean, standard deviation (SD), median, Q1, Q3, minimum, and maximum. For PK endpoints, the coefficient of variation (CV), geometric mean, and geometric CV will also be provided.

Categorical variables will be presented as frequencies and percentages. The AE tables will also present the within-arm summary measure of EAIR; expressed as number of subjects with events per 100 subject exposure years.

 Innovaderm Research 	STATISTICAL ANALYSIS PLAN, Final Version 1.0
Protocol Number: ARQ-151-313	Sponsor: Arcutis Biotherapeutics, Inc.

Summary tables will be presented by visit, when applicable, and treatment group (refer to Section 5).

5.7 Statistical Tests

No hypothesis tests are planned for this study; therefore p-values will not be provided. For estimation purposes, two-sided 95% confidence interval (CI) will be supplied for secondary efficacy endpoints and EAIRs.

5.8 Handling of Retests, Unscheduled Visits, and Early Termination Data

Retests measurements, unscheduled measurements, and ET visit assessments will be included in analysis and be summarized via analysis visit windowing according to the windowing conventions in section 5.4.

5.9 Software Version

All analyses will be performed using SAS® software Version 9.4 or higher.

6 STATISTICAL CONSIDERATIONS

6.1 Adjustments for Covariates

There will be no adjustment for covariates when performing summaries for this study.

6.2 Handling of Dropouts or Missing data

See [Appendix 2](#) for handling of completely or partially missing dates for prior and concomitant medications and AEs.

Unless otherwise specified, missing safety data will not be imputed.

6.2.1 Multiple Imputation

For the vIGA-AD secondary efficacy endpoints (refer to Section 12.2), vIGA-AD non-imputed values collected during the parent studies and this study (including the last available data of subjects who prematurely withdraws from this study) will be appended together after having been assigned to pre-specified analysis visit using the analysis windows defined in their respective study (parent study SAPs or this SAP Section 5.4, as applicable). Doing so, each subject will have between 4 (subjects who enrolled in OLE and discontinued early before the first application of

 Innovaderm Research	STATISTICAL ANALYSIS PLAN, Final Version 1.0
Protocol Number: ARQ-151-313	Sponsor: Arcutis Biotherapeutics, Inc.

roflumilast cream during the OLE study) to 7 (subjects in Cohort-Week 24 who completed the OLE) or 9 (subjects in Cohort-Week 52 who completed the OLE) vIGA-AD non-imputed values:

OLE Analysis Visit	Study/Analysis Visit
OLE Week -4	Parent study derived baseline value (refer to parent study Section 5.2)
OLE Week -3	Parent study / analysis visit Week 1
OLE Week -2	Parent study / analysis visit Week 2
OLE Day 1	Parent Study / analysis visit Week 4
OLE Week 4	OLE study / analysis visit Week 4
OLE Week 12	OLE study / analysis visit Week 12
OLE Week 24	OLE study / analysis visit Week 24
OLE Week 36*	OLE study / analysis visit Week 36
OLE Week 52*	OLE study / analysis visit Week 52

* Cohort-Week 52 subjects only.

Note: No missing data are expected for the OLE Week -4 to OLE Day 1 analysis visits since subjects must have completed a parent study to be eligible for enrollment in this OLE study.

Then, to comply with the definition of the parent studies' primary estimand (refer to parent studies Section 12.1.1), efficacy data assigned to a pre-specified analysis visit will be removed from the source data used for the multiple imputation process if subject's last dose day falls within the analysis visit window or is prior to the start of the analysis visit window used to assign data to a pre-specified analysis visit (refer to Section 12.2) for subjects who discontinued due to lack of efficacy or adverse event. This procedure will ensure that the data collected on or after intercurrent events are not used in the imputation process.

vIGA-AD missing values will be imputed before deriving the vIGA-AD secondary efficacy endpoints (refer to Section 12.2), using a Predictive Mean Matching (PMM) sequential-regression multiple imputation model for the Full Analysis Set population as per the following three-step process.

1. The first step is to understand the pattern of missingness. In order to perform the multiple imputation, a monotone missing pattern has to be achieved. For example, if there exist values for OLE Week 4 and OLE Week 24 visits, but missing values for the OLE 12 visit, the Markov-Chain Monte-Carlo (MCMC) method will be used to impute the small amount of missing data that may be missing at the intermediate visits that is required to make the missing data pattern monotone before applying the multiple imputation algorithm. This

 Innovaderm Research	STATISTICAL ANALYSIS PLAN, Final Version 1.0
Protocol Number: ARQ-151-313	Sponsor: Arcutis Biotherapeutics, Inc.

method uses a non-informative Jeffreys prior to derive the posterior mode from the expectation-maximization (EM) algorithm as the starting values for the MCMC method. The MCMC method will use the seed 6457149. The model will include the parent study randomized vIGA-AD stratification variable and parent study randomized treatment group (refer to Section 5.5), both as categorical variables, as well as all vIGA-AD scores collected at scheduled visits during both the parent and OLE studies, all as continuous variables. To avoid values that could not be observed in practice, imputed values will be rounded to the nearest integer (Round=1 option in PROC MI) in the range of 0 to 4.

To determine the number of multiply imputed datasets to be created at this step, the proportion of datapoints with non-monotone pattern across all visits and subjects will first be derived as follows:

$$\frac{\text{number of non monotone visits accross all visits and subjects}}{\text{total number of expected visits accross all subjects}} * 100$$

Of note, the total number of expected visits across all subjects is not the same for the Cohort-Week 24 subjects and Cohort-Week 52 subjects i.e., 7 visits during the OLE study for Cohort-Week 24 subjects and 9 visits during the OLE study for the Cohort-Week 52 subjects.

Then, the following table will be used:

Non-monotone Missing Data	Number of Imputed Datasets
$\leq 2\%$	1
$> 2\% \text{ to } \leq 5\%$	3
$> 5\%$	10

- Once the monotone pattern is achieved, the next step is to implement the imputation algorithm. For this, the PMM regression method will be used. This method is particularly helpful if the normality assumption is violated. For subjects with complete data up to a particular visit, a PMM regression model will be fit that includes the outcome at that visit as the dependent variable and as independent variables, the parent study randomized vIGA-AD stratification variable and parent study randomized treatment group, both as categorical variables, as well as the vIGA-AD score outcomes at previous analysis visits, all as continuous variables, using a seed of 482371. This process will be repeated 25 times, resulting in a total of 25 to 250 complete analysis datasets, depending on the number of

 Innovaderm Research	STATISTICAL ANALYSIS PLAN, Final Version 1.0
Protocol Number: ARQ-151-313	Sponsor: Arcutis Biotherapeutics, Inc.

imputed monotone datasets that are required. The seed may be changed after unblinding in case of any issues with the imputation process, and it will be documented in the CSR if any change is required.

3. For each multiply imputed dataset, Primary or OLE Baseline values, as applicable, will be derived as defined Section 5.2 and analysis visits from parent studies (OLE Week -4 to OLE Day 1) not selected as Primary or OLE Baseline, as applicable, will be dropped from each multiple imputed dataset.

For Cohort-Week 24 subjects, imputed OLE Week 36 and Week 52 analysis visit values will be set to missing given that these subjects will complete study at Week 24 or discontinue early from study before Week 24, whichever occurs first.

Finally, for each completed dataset, the vIGA-AD secondary efficacy endpoints will be derived by visit, as described in Section 12.2. Common proportion of success/achievement (and associated standard error [SE]) will then be calculated overall and by treatment group for each OLE analysis visit and combined using PROC MIANALYZE based on Rubin's rule to obtain a combined common proportion of success/achievement for each OLE analysis visit overall and treatment group. The combined common two-sided 95% CI will be calculated as per Lott and Reiter (2020)¹ multiple imputation Wilson interval method

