5.4 Windowing Conventions

The scheduled visit will be used to report measurements for summaries by visit regardless of whether this visit was performed within or outside of the analysis visit windows. Unscheduled visit, early termination (ET) visit, and/or retest measurements will only be used for the summaries by visit if a scheduled measurement is not available and the unscheduled/retest/ET measurement

 Innovaderm Research	STATISTICAL ANALYSIS PLAN, Final Version 1.0
Protocol Number: ARQ-151-313	Sponsor: Arcutis Biotherapeutics, Inc.

falls within the analysis visit windows described in [Table 3](#), [Table 4](#), [Table 5](#), and [Table 6](#). Scheduled, unscheduled, ET, and retest measurements will be listed.

If there is more than one assessment for a given analysis visit when a scheduled measurement is not available, the assessment closest to the target day will be considered. If two assessments are equidistant to the target day, the latest assessment will be used.

Table 3 OLE Analysis Visit Windows – vIGA-AD, EASI, BSA Affected by AD, DLQI, CDLQI, IDQOL, DFI, SCORAD, POEM, Vital Signs, Local Tolerability Assessments, PHQ-8, PHQ-A, CDI-2, and C-SSRS

Analysis Visit	Target Day	Window (Days)
OLE Week 4	29	15 to 57
OLE Week 12	85	58 to 127
OLE Week 24	169	128 to 211
OLE Week 36	253	212 to 309
OLE Week 52	365	≥ 310

Table 4 OLE Analysis Visit Windows – WI-NRS

Analysis Visit	Target Day	Window (Days)
OLE Week 1	8	5 to 11
OLE Week 2	15	12 to 18
OLE Week 3	22	19 to 25
OLE Week 4	29	26 to 32
OLE Week x	y	z1 to z2
OLE Week 52	365	≥ 362

where: x= 5 to 51; y= (x * 7) + 1; z1 = y – 3, and z2 = y + 3.

Table 5 OLE Analysis Visit Windows – Clinical Laboratory

Analysis Visit	Target Day	Window (Days)
OLE Week 24	169	15 to 267
OLE Week 52	365	≥ 268

 Innovaderm Research	STATISTICAL ANALYSIS PLAN, Final Version 1.0
Protocol Number: ARQ-151-313	Sponsor: Arcutis Biotherapeutics, Inc.

Table 6 OLE Analysis Visit Windows – Physical Examination

Analysis Visit	Target Day	Window (Days)
OLE Week 4	29	15 to 127
OLE Week 24	169	128 to 267
OLE Week 52	365	≥ 268

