5.5 Derived Variables

All questionnaire scores will be derived by Biostatistics in the ADaM datasets using the formulas defined below, even if calculated scores are present in the EDC database. All pre-calculated scores will be ignored for analysis.

- With the following exception, vIGA-AD Score of Clear (0) or Almost Clear (1) = vIGA-AD of ‘Clear’ (0) or ‘Almost Clear’ (1). The exception is that for subjects who discontinued early from study due to an AE or lack of efficacy, the subject will be considered as not having a vIGA-AD score of Clear (0) or Almost Clear (1) for all pre-specified analysis visits (refer to Section 5.4) for which the subject’s day of last dose falls within or is before the start of the analysis visit window.
- With the following exception, vIGA-AD Success = vIGA-AD of ‘Clear’ (0) or ‘Almost Clear’ (1) plus at least a 2-grade improvement from baseline. The exception is that for subjects who discontinued early from study due to an AE or lack of efficacy, the subject will be considered as not having a vIGA-AD success for all pre-specified analysis visits (refer to Section 5.4) for which the subject’s day of last dose falls within or is before the start of the analysis visit window. vIGA-AD Success will be derived for both the Primary and OLE baselines (refer to Section 5.2)
- Date of last contact = the latest of last study visit date, last dose date, end-of-study date and end-of-treatment date.
- Post-OLE Week 4 study duration (days): The duration can be represented as End Date – Start Date +1. The start date of the Post-OLE Week 4 interval will be the date of the OLE Week 4 visit or OLE Day 29 if the subject missed the OLE Week 4 visit. The end date will be the date of last contact. This endpoint will be calculated only for subjects who enter the post-OLE Week 4 study period.
- Duration (days) of the first BIW dosing will be calculated from the first BIW dosing to the start of the succeeding QD dosing interval. Subject’s last contact date will be used to censor

 Innovaderm Research	STATISTICAL ANALYSIS PLAN, Final Version 1.0
Protocol Number: ARQ-151-313	Sponsor: Arcutis Biotherapeutics, Inc.

this endpoint (time-to-event analysis) or as the end date of this duration (analyzed as a continuous endpoint) for subjects who do not revert to a QD dosing regimen after the first BIW dosing. This endpoint will be calculated only for subjects who enter the post-OLE Week 4 study period with at least one BIW dosing interval.

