12.2.2 Sensitivity Analyses

As sensitivity analyses to the imputation method used for the main analysis of the vIGA-AD endpoints (refer to Section 12.2.1), the main analysis of these endpoints will be repeated, but using the following imputation method:

- Non-responder imputation (refer to Section 6.2.2)
- Observed cases (i.e., no imputation)

No sensitivity analyses will be performed for the secondary efficacy endpoints based on WI-NRS and EASI total score.

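### The failure-and-deletion rule for subjects stopping for AE or lack of efficacy works by visit window, not assessment date, so some on-treatment vIGA-AD responses count as failures and some post-treatment scores could survive

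*SAP*

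**What the plan says.** SAP 5.5 (Derived Variables) defines vIGA-AD 0/1 and vIGA-AD success with one exception. A subject who leaves early because of an AE or lack of efficacy is a non-responder at every analysis visit for which the "day of last dose falls within or is before the start of the analysis visit window".

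SAP 6.2.1 (Multiple Imputation) removes the same visits from the imputation source data. The trigger there is that the "last dose day falls within the analysis visit window or is prior to the start of the analysis visit window used to assign data", and it applies "for subjects who discontinued due to lack of efficacy or adverse event". Two reasons are given: compliance with the parent studies' primary estimand, and the assurance that "This procedure will ensure that the data collected on or after intercurrent events are not used in the imputation process".

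SAP 5.4 (Windowing Conventions), Table 3, sets the vIGA-AD windows. The same section assigns scheduled visits by their nominal label: "The scheduled visit will be used to report measurements for summaries by visit regardless of whether this visit was performed within or outside" the window.

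SAP 12.2.2 repeats the main vIGA-AD analysis with non-responder imputation and with observed cases. Neither repeat lifts the exception in 5.5.

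**The concern.** Both rules ask where the last dose lies relative to a window. Neither asks whether the score was taken before or after that dose. In a study with visits 8 to 16 weeks apart, a window can stay open for weeks after its visit has taken place. A genuine on-treatment response can therefore be reported as a failure because of a window boundary, and not because of the subject's response or exposure.

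The opposite slip is also possible. A scheduled visit keeps its label when held outside its window, so one held after both the window's end and the last dose is not caught.

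At stake are the by-visit proportions for two secondary endpoints. Because the exception is part of the endpoint definition, the two planned sensitivity analyses change only the handling of missing values and cannot show its effect.

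**Working it through.** **Inputs.** Target days and windows are from SAP 5.4, Table 3. Visit tolerances (±3 days at Week 4, ±7 days afterwards) are from Protocol 1.3.

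**The plan's own figures.** Window ends are midpoints between adjacent targets: (29+85)/2 = 57; (85+169)/2 = 127; (169+253)/2 = 211; (253+365)/2 = 309. The first window starts at (1+29)/2 = 15. All match Table 3.

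| Visit | Target day | Window | Length (days) | Days open after target |
|---|---|---|---|---|
| Week 4 | 29 | 15-57 | 43 | 57-29 = 28 |
| Week 12 | 85 | 58-127 | 70 | 127-85 = 42 |
| Week 24 | 169 | 128-211 | 84 | 211-169 = 42 |
| Week 36 | 253 | 212-309 | 98 | 309-253 = 56 |

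The Week 52 window is open-ended from Day 310. An on-target visit on Day 365 adds no affected days.

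**Example, valid score lost (Cohort-Week 52).** A subject scores 0 at Week 24 on Day 169 and takes the last dose on Day 205, stopping for an AE. Day 205 lies in 128-211, so the score is failed and deleted although it was taken 205-169 = 36 days before the last dose. With a last dose on Day 212, the same score is kept.

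**Example, late score kept.** A scheduled Week 12 visit is held on Day 130, after a last dose on Day 128. The visit is still labelled Week 12. Day 128 is neither inside nor before 58-127, so the post-treatment score stays. This needs a visit far outside the protocol tolerance (85±7, that is Days 78-92), so it should be rare.

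**Share of last-dose days affected, on-target visits.**
- Cohort-Week 52: 28+42+42+56 = 168; 168/365 = 46%.
- All four visits at the late limit of tolerance: 25+35+35+49 = 144; 144/365 = 39%. All at the early limit: 31+49+49+63 = 192; 192/365 = 53%.
- Cohort-Week 24: 28+42 = 70; 70/169 = 41%.

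**Effect on a visit's responder proportion.** Shift = d × (x/365) × r. Here d is the share stopping for AE or lack of efficacy over 52 weeks, spread evenly; x is the number of days the window stays open after target; r is the responder share among affected subjects. The documents give neither d nor r. The assumed ranges are d = 2-10% and r = 20-50%.
- Smallest: 0.02 × 28/365 × 0.20 = 0.0003, or 0.03 points.
- Largest: 0.10 × 56/365 × 0.50 = 0.0077, or 0.8 points.
- If all such stops fell within Days 15-309 (43+70+84+98 = 295 days), the largest becomes 0.10 × 56/295 × 0.50 = 0.0095, or 0.95 points.

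The shift scales in proportion to d, so a higher or front-loaded rate raises it.

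**Role of the deletion.** The affected subject's own outcome is already fixed as a failure by 5.5. Removing the score changes only the imputation regression and donor pool. If the removed scores are mostly poor ones, this may push imputed response upwards, against the direction of the failure rule.

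**The case against.** The strongest defence is that the window rule is deliberate. SAP 6.2.1 ties it to the parent studies' primary estimand, and the rule is written out consistently for both endpoints and for the imputation. Read as a composite strategy, stopping for an AE or lack of efficacy fails the whole analysis visit, and no score is misclassified. The parent SAPs are not available here, so this cannot be excluded. However, SAP 6.2.1 shows the parent post-baseline visits at Weeks 1, 2 and 4, at most two weeks apart. A rule that does little harm on that schedule does not carry over soundly to windows of 43 to 98 days, and the SAP nowhere says that failing the whole window is intended.

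A reader might infer that the SAP contradicts itself by deleting scores taken before the event. The documents do not support that. The quoted assurance runs one way: later data will not be used. It does not promise that only later data will go. The assurance is not strictly met only in the late-visit case.

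It is also fair to say that the last dose is not always the date of the event, since an AE or loss of efficacy can precede it. That stands, but last dose is the SAP's own marker, and a date-based rule uses the same one.

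Finally, the affected scores remain visible elsewhere. Change in vIGA-AD, the EASI summaries and the vIGA-AD duration endpoints use recorded scores and do not state the exception. That limits the consequence, but it also means the Day 169 score in the example would count as time clear in one table and as a failure in another.

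**Conclusion.** The point holds as a design weakness in the main analysis of the two vIGA-AD secondary endpoints. The rule takes in some valid on-treatment responses and can miss a late post-treatment score. It touches only subjects who stop for an AE or lack of efficacy, and on-treatment scores are lost only when the last dose falls after the visit and before its window closes. Cohort-Week 24 cannot produce the Day 205 example or any Week 36 effect.

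The likely size is a downward shift below about 1 point per visit, on the assumed rates above. A reader might infer 1 to 2 points, but the upper end requires every affected subject to be a responder: 0.10 × 56/295 = 1.9 points. Overwriting a score of 2 or more changes nothing, and subjects stopping for lack of efficacy are unlikely to be responders. The net direction is not certain, because the deletion may act the other way.

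SAP 5.7 plans no hypothesis tests, so no decision turns on this. It is worth correcting because all three versions of the vIGA-AD result inherit it.

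**What to change.** In SAP 5.5 and 6.2.1, for subjects who stop for an AE or lack of efficacy:
- Set to non-response, and remove from the imputation input, only assessments dated after the last dose, plus all later analysis visits. Include nominal visits held outside their windows. State that a visit not yet assessed by the last dose counts as later.
- Keep scheduled assessments dated before the last dose.
- State how an assessment on the last-dose day is handled, consistently with the stated aim, which covers data from the day of the event as well as after it.
- Correct the cross-reference in 6.2.1 for the windows from Section 12.2 to Section 5.4.

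The cost is a few sentences and some reprogramming. The dates needed are already used for Study Day and exposure. The downside is a small departure from the parent-study wording. If exact alignment matters, the window-based result can be kept as a sensitivity analysis.

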4 POPULATIONS FOR ANALYSIS

4.1 Full Analysis Population

The full analysis population is defined as all subjects who are enrolled in this study.

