5 GENERAL CONSIDERATIONS

Formats and layouts of tables, listings, and figures (TLFs) will be provided in a separate document (output general layout is described in [Appendix 1](#)).

For analysis purposes, the TLFs will be summarized overall and by previous treatment group in the parent studies as indicated below. Rollovers from the ARQ-151-311/312 studies will be summarized separately from rollovers from the ARQ-151-315 study.

- Rollovers from ARQ-151-311/312 studies
 - Roflumilast cream 0.15%
 - Vehicle / Roflumilast cream 0.15%
 - Pooled Roflumilast cream 0.15%
- Rollovers from ARQ-151-315 study
 - Roflumilast cream 0.05% or 0.15%
 - Vehicle / Roflumilast cream 0.05% or 0.15%
 - Pooled Roflumilast cream 0.05% or 0.15%

 Innovaderm Research	STATISTICAL ANALYSIS PLAN, Final Version 1.0
Protocol Number: ARQ-151-313	Sponsor: Arcutis Biotherapeutics, Inc.

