6.3 Interim Analyses

An IA of data collected in this study will be performed after the database lock and study unblinding of parent studies ARQ-151-311 and ARQ-151-312. Only data from subjects that rolled over from one of these two parent studies into study ARQ-151-313 will be included in this IA. That is, in order to preserve the blind of parent study ARQ-151-315, which will still be ongoing at the time of ARQ-151-311 and ARQ-151-312 database lock and study unblinding, no data from subjects enrolled in parent study ARQ-151-315 that have rolled over into study ARQ-151-313 will be included in this IA.

Another IA may be conducted at the time of rollovers from these two parent studies complete all scheduled visits in ARQ-151-313. If conducted, similarly to the first IA, only data from subjects

 Innovaderm Research	STATISTICAL ANALYSIS PLAN, Final Version 1.0
Protocol Number: ARQ-151-313	Sponsor: Arcutis Biotherapeutics, Inc.

that rolled over from one of these two parent studies into study ARQ-151-313 will be included in the IA in order to preserve the blind of parent study ARQ-151-315.

All analyses planned in this SAP will be performed at the time of the IA.

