12.2.3 Subgroup Analyses

The main analysis of the secondary efficacy endpoints of vIGA-AD score of clear (0) or almost clear (1) and vIGA-AD success (refer to Section 12.2.1) will be repeated for each of the subgroups mentioned in Section 6.6. Subgroup analyses will only be conducted for results relative to the primary baseline only.

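### The single vIGA-AD imputation model has no age term and leaves the coding of the two vehicle arms undefined, although results are reported by parent program and by age group

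*SAP*

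**What the plan says.** SAP Section 6.2.1 specifies a "sequential-regression multiple imputation model for the Full Analysis Set population". SAP Section 4.1 adds: "The full analysis population is defined as all subjects who are enrolled in this study". At the final analysis the imputed population is therefore all rollovers from ARQ-151-311, 312 and 315. No sentence splits the imputation by program. A single run is inferred from this and is not stated in words.

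The matching model at each visit contains "the parent study randomized vIGA-AD stratification variable and parent study randomized treatment group, both as categorical variables". Its other predictors are the subject's scores from earlier visits, entered as continuous. The preceding MCMC step uses the same two categorical terms and refers to Section 5.5 for the treatment group. Section 5.5 lists derived variables and defines no treatment group; Section 5 and Appendix 1 do.

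On reporting, Section 5 states: "Rollovers from the ARQ-151-311/312 studies will be summarized separately from rollovers from the ARQ-151-315 study". Under Section 12.2.3 the imputed main analysis of both vIGA-AD secondary endpoints "will be repeated for each of the subgroups mentioned in Section 6.6", and Section 6.6 lists age group first (2-5, 6-11, 12-17, 18 and over).

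Two further rules matter. Section 5.5 counts subjects who stop for an adverse event or lack of efficacy as failures from the visit window containing their last dose onward. Section 12.2.2 repeats the analysis with non-responder imputation and with observed cases.

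**The concern.** Predictive mean matching fills a gap with the observed score of a subject whose predicted score is close. If a variable that defines a reported group is not in the model, two subjects with the same history but from different groups get the same prediction, and either can be the donor. When the groups truly differ given that history, each group's imputed scores move toward the other's.

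This can happen in two places:

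- **Vehicle arms.** If vehicle is one level, former-vehicle subjects aged 2-5 on 0.05% and former-vehicle subjects aged 6 and over on 0.15% share an intercept and a donor pool.
- **Age within 311/312.** No term carries age, and the donors available late in the study are older than the children being imputed.

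At stake are the main-analysis proportions for vIGA-AD 0/1 and vIGA-AD success at later visits, by program column and by age subgroup. There is also a consistency question. Section 6.3 says: "Another IA may be conducted at the time of rollovers from these two parent studies complete all scheduled visits". If that interim is held, the imputed 311/312 results could change at the final analysis without new 311/312 data, because 315 subjects have joined the model.

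**Working it through.** **1. The plan's own figure.** The only figure in Section 6.2.1 that can be checked is the number of completed datasets: 25 × 1, 3 or 10 = 25, 75 or 250. This matches the stated 25 to 250 and is not in dispute.

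**2. Which reported splits does the model carry?**

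| Reported split | Term carrying it | Separated? |
|---|---|---|
| 311/312 active v 315 active | Randomized arm (0.15% only in 311/312, 0.05% only in 315) | Yes |
| 311/312 vehicle v 315 vehicle | Randomized arm, if coded as the Section 5 groups | Undefined |
| Age 6-11, 12-17, 18 and over | None | No |
| Baseline vIGA-AD 2 v 3 | OLE Week -4 score and stratum | Yes |
| Sex, race, ethnicity, prior corticosteroid response, facial involvement | None | No |

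Six of the seven general subgroup variables are absent. On the vehicle arms, Appendix 1 gives the parent-study treatment as Vehicle in both programs but gives two different output names, so either coding can be read from it.

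**3. Donors at Weeks 36 and 52.** Cohort-Week 24 is aged 6-17 (SAP 3.1) and ends at Week 24. The protocol's summary of changes puts it at about 275 + 275 = 550. The 311/312 donors left are adults and those aged 6-17 in Cohort-Week 52. Their split is not given.

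**4. Size.** Shift in a reported rate = fraction missing × error among the imputed. A rough ceiling is fraction missing × true gap between the groups. With assumed missingness of 20-30% and an assumed gap of 10-20 points (60% v 40-50%), the ceiling is 0.20 × 10 = 2 to 0.30 × 20 = 6 points. Earlier scores in the model absorb part of it.

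*Vehicle coding, one visit.* Simulation inputs: N = 1500 (Protocol 6.2). Assumed: 400, 550 or 700 from 315; 2:1 active to vehicle; 20% missing; five nearest donors; 315 worse by 0, 0.3 or 0.5 grade given the same history. Error is in points among imputed 315 subjects.

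| Coding | Active: cross-program donors; error | Vehicle: cross-program donors; error |
|---|---|---|
| One vehicle level | 9-21%; within 0.7 | 54-73%; +6.8 to +15.8 with a shift, -1.7 to +0.9 without |
| Two vehicle levels | 9-20%; within 1.2 | 18-34%; within 1.2 |
| Separate by program | 0%; -1.4 to +0.8 | 0%; -0.8 to +0.4 |

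For the reported 315 vehicle column with one level, this is 0.20 × 6.8 = 1.4 to 0.20 × 15.8 = 3.2 points. That is an upper edge: the shift appears only at the imputed visit, so history carries none of it, and the failure rule is not applied.

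*Vehicle coding, sequence to Week 52.* Several sets of assumed inputs (60% v 40-50% true rates, 20-30% dropout) with one vehicle level give +0.2 to +2.0 for 315 vehicle and -0.4 to -2.4 for 311/312 vehicle. If half of the dropouts fall under the failure rule (assumed; about 22% dropout), 311/312 vehicle is off by -0.9 (60% v 40%) or 0.0 (60% v 50%), and 315 vehicle by +0.7 or +0.4. With two vehicle levels the errors are within 0.5.

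*Age.* Assumed: 100 children and 300 adults from 311/312 in Cohort-Week 52, 550 from 315, 60% true rate in adults and 40-50% in children, 20-30% missing.

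- Two vehicle levels, no age term: 311/312 children +1.3 to +3.4; the child-adult gap shrinks by 1.6-4.6 points.
- Split by program only: children +1.2 to +4.0.
- Imputed within age group: all errors at most 0.5.

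**5. Scale.** At the same assumed sizes, the vehicle columns at Week 52 hold about (950 - 550)/3 = 133 and 550/3 = 183 subjects. The 95% half-widths are about 1.96 × √(0.6 × 0.4/133) = 8.3 and 1.96 × √(0.6 × 0.4/183) = 7.1 points.

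**The case against.** The strongest reply is that little rides on this. The endpoints are secondary and descriptive in a single-arm safety study, and SAP Section 5.7 plans no tests. Two sensitivity analyses use no donors at all. The failure rule in Section 5.5 fixes adverse-event and lack-of-efficacy dropouts whatever is imputed, so donors matter only for the rest. The shifts are well below the half-widths in step 5. Every size depends on inputs the documents do not give, and vanishes if programs and ages do not differ given earlier scores. All of that stands, and it sets the severity. It does not make the model adequate: the sensitivity analyses replace the missing-data assumption and cannot show whether the main imputation is well specified.

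A reader might also infer stronger claims that the documents do not support:

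- *The model ignores parent program.* It does not in the active arms, where randomized arm identifies the program.
- *Every subgroup variable is missing.* Baseline vIGA-AD is a listed subgroup and is in the model.
- *Scores of 2-5-year-olds are filled from older subjects.* They can be. Same-program subjects are donors too, and the active arms show no material error.
- *The vehicle arms are merged.* The SAP leaves the coding open; with the Section 5 groups the vehicle error largely goes.
- *The interim results are affected across programs.* The interims exclude 315. The interim-to-final shift needs a second interim that is only optional.

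**Conclusion.** The point holds as a minor specification gap with two parts. First, the SAP does not say whether the two vehicle arms form one level or two, and its cross-reference defines neither. With one level, and a true program difference given history, the reported vehicle columns move toward each other by about 0-2 points. Second, under any coding the model has no age term, while 6-17-year-olds from 311/312 can be filled largely from adults at Weeks 36 and 52. If age matters given earlier scores, their reported rates shift by about 1-4 points toward the adults.

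Both sizes rest on assumed program sizes, response rates, correlation and dropout. They are smaller once the failure rule is applied. The documents support the direction, not a particular number.

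**What to change.** In SAP Section 6.2.1:

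- State that both imputation steps (MCMC and predictive mean matching) run separately for 311/312 and 315 rollovers. These are never reported together, so nothing is lost in the tables, and the interim and final 311/312 models then use the same population.
- Add age group (6-11, 12-17, 18 and over) as a categorical term in the 311/312 model. The split by program does not replace this: alone, it left the children's error in place. The run that removed that error imputed within age groups; a model term should act in the same way as separate arm levels did for vehicle.
- Point the treatment-group reference to Section 5 instead of Section 5.5.

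Adding the other subgroup variables is optional.

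The cost is SAP wording and a BY statement; all the variables are already collected. The downside is a smaller donor pool in each model.
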